#### Location of Research

All data collection and research analyses will take place in an air-conditioned research lab (Rm. 268) fully equipped with all systems necessary to obtain color vision performance data (UIW Rosenberg School of Optometry, [name]). Informed consent may occasionally be administered in and adjacent study room.

---

#### Purpose

The long-term objectives of this study is to extend upon our initial research (Rabin, J., Silva, F., Trevino, N. et al. Performance enhancement in color deficiency with color-correcting lenses. *Eye* 36, 1502–1503 (2022). <https://doi.org/10.1038/s41433-021-01924-0>) in which we showed improvements in CVDs with CCLs and after wearing CCLs. But the spectacles varied significantly between CVDs (some outdoor, some indoor), control measures were minimal, there were limitations on the full impact of brainwave measures and new and improved CCLs have just been introduced which apply to both green and red color deficiency. Moreover, we found that potential changes in the brain can occur from wearing these lenses in as little as 1 week or even less vs. what we reported thus far in the seminal research of Werner and colleagues (Werner JS, Marsh-Armstrong B, Knoblauch K. Adaptive Changes in Color Vision from Long-Term Filter Usage in Anomalous but Not Normal Trichromacy, *Current Biology*, 2020, 3011-3015. <https://doi.org/10.1016/j.cub.2020.05.054>) which only reported 12 day results. Finally, we wish to conduct our comprehensive vision research to correct limitations stated above AND within the proper parameters of a randomized clinical trial in which proper controls will be implemented for ALL CVD subjects to reach more definitive conclusions. Hence we wish to evaluate a larger sample of CVD subjects with a design which minimizes sources of variability, includes controls, and tests that better account for real-world performance. Moreover, we are recording both brainwaves and eye-waves to assess the retina, optic nerve and brain to localize where changes may be occurring in the visual system in responses to wearing CCLs. Finally, we believe these lenses have potential occupational applications for CVDs excluded from certain jobs as well as in acquired CVD from eye and other diseases.

## Equipment to Be Used

1. Precision Vision, Inc. "Super Vision Test" to measure high contrast visual acuity (VA) and Small Letter Contrast Sensitivity (CS).
2. Oculus HMC red-green anomaloscope to diagnosis color vision normal (CVN) and color vision deficiency (CVD) individuals.
3. Ishihara 15-plate color vision book tests to diagnose CVN vs. CVD subjects.
4. Cone Specific Contrast Sensitivity Test (CCT, Innova Systems, Inc.) administered on a calibrated Microsoft Surface Display.
5. Cone Contrast Naming Test administered on a calibrated Microsoft Surface Display.
6. Cone specific VA, small letter CS, and large letter CS administered on a calibrated Microsoft Surface Display.
7. Cone Specific Supra-threshold Color Matching Test administered on a calibrated Microsoft Surface Display.
8. "Cockpit" color identification test displayed on a 17" calibrated LCD monitor.
9. Cone specific visual brainwaves (visual-evoked potentials VEPs) and flash and pattern eye waves (electroretinograms, ERGs) recorded from a large LCD monitor (Diagnosys, LLC). Ear clip, surface and ERG electrodes DTL fiber electrodes (Diagnosys, LLC) will be used for recordings after appropriate cleansing of surface skin areas and application of conductive electrode paste as specified in detail in the methodology section.
10. All CVD subjects will be tested with and without the newest indoor version of the EnChroma color vision correcting lenses ([www.enchroma.com](http://www.enchroma.com)) as well as placebo neutral gray lenses which transmit the same amount of visible light but do not alter color) in a registered randomized clinical trial with crossover (to be explained in methodology and design sections). Five CVN control subjects will also be tested with the EC lenses on the same battery of tests to determine if they alter color vision for CVNs, and 15 CVNs will be tested without CCLs or placebo lenses on the computer-based letter charts and electro-diagnostic tests to establish normative values for these tests.

## Duration

We are requesting a total of 2 years for subject recruitment, comprehensive testing, data analyses and preparation of multiple abstracts for research presentation and multiple papers to submit for peer-reviewed publication.

## Funding

The research and majority of researchers are being funded internally. Two student researchers ([name] and [name]) are being funded for by our NIH/NEI T35 Research Grant #1T35EY032441-01A1. EnChroma ([www.enchroma.com](http://www.enchroma.com)) is donating CCLs and placebo lenses to each CVD subject and two pair to use in-house for color measurements but is providing no funding or is involved in the design, data collection or data analyses.

## Financial Conflict of Interest

---

Does any member of the project team hold financial interest in the funding organization or any similar organization (stocks, board membership, etc)?

- Yes  
 No
-

## Hypothesis

**Null Hypothesis:** CCLs have no significant impact on color vision performance in CVDs.

**Experimental Hypothesis:** CCLs can promote immediate improvement in color vision performance in CVDs and performance after one-week of daily wear. As reported previously, performance enhancement after one week of wear may persist if when not wearing the lenses indicating possible neuro-adaptive change.

## Statistical Design and Analysis

A double blind randomized clinical crossover trial will be used to assess the immediate and long-term effects on color vision of CCLs in CVDs. Parametric within and between subjects ANOVA with post-hoc t-tests corrected for multiple comparisons will be utilized with primary focus on within-subject comparisons including normal vs. defective cone responses. Although subjects who wear the CCL lenses during week one may show carry-over of this exposure to week two when wearing the placebo lenses, we believe this may offer additional insight into the time course and longevity of any effects from presumed neuro-adaptive changes.

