## Background and Review of Literature

Normal color vision (CVN) depends on normal red, green, and blue sensitive cone photoreceptors. 8% of males and 0.5% (1/200) females are color vision deficient (CVD), a non progressive hereditary condition in which the red or green cone is missing, or more commonly shifted in peak color sensitivity making it more difficult to tell colors apart and correctly identify colors (1,2). In addition to hereditary CVD, color vision can be decreased at a clinical or subclinical level as an early sign of ocular, systemic and/or neurological disease. (3-7). CVN is required for aviation, military specialties, transportation, and law enforcement wherein color identification and discrimination may be the only cue for critical decisions (3,4). A novel approach using notch filter spectacles (selective wavelength blocking filters to increase differences in stimulation to red and green cones) was implemented by EnChroma®. Extended use by CVDs for two weeks demonstrated improvements in red-green color perception even without wearing the glasses at the 2-week testing point indicating possible neuro-adaptive/brain changes (8). We extended this evaluation by including both threshold (just visible) and supra-threshold testing (readily visible) and found similar results (11). However, a major difference was that our testing was cone specific allowing us to more specifically compare findings from the defective and normal cones in red and green cone CVDs. Limitations of our initial pilot study included a large variability in the type of CCL glasses used (outdoor vs. indoor, red vs. green specific). In addition, since we previously demonstrated enhanced binocular VEP responses in CVDs suggesting neural compensation without CCLs (10), we will be conducting monocular VEP and ERG cone specific tests on all subjects to better identify CCL induced immediate and long term changes on retinal, optic nerve and cortical objective responses. Finally, no study thus far using these CCLs has adhered to the tenets of a registered randomized clinical control cross-over design which we are conducting to definitively address the findings presented in prior studies.

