## Methods

After study briefing and subject provision of written informed consent, the following sequence of tests will be conducted. Half of the 20 CVD subjects will be randomized to initial treatment (CCLs) and half to initial or control groups (placebo neutral lenses). Baseline testing will be conducted with and without the lenses, then be requested to wear the lenses for a minimum of three hours per day, followed by retesting with/without lenses 7 days later. On the next 1-3 days the subject will then: cross-over to the lens not yet worn, undergo testing, and be tested again 7 days later. Neither subjects or Interns administering the tests will be aware of which lenses the subject is wearing (double-blind clinical trial). On all tests the order of testing with with and without lenses will be randomized across subjects to control for potential order effects. Those tests marked by an asterisk will be retested on CVD subjects during each session. Additional controls for order effects are specified below.

1. Precision Vision, Inc. "Super Vision Test" to measure high contrast visual acuity (VA) and Small Letter Contrast Sensitivity (CS) in right and left eyes at 4m in a darkened room; only at baseline.
2. Oculus HMC anomaloscope to diagnosis CVN and CVD subjects; only at baseline.
3. Ishihara 15-plate (14 testable plates, one demo) color vision book test to diagnose CVN vs. CVD; only at baseline.
4. \*Cone Specific Contrast Sensitivity Test (CCT, Innova Systems, Inc.) administered binocularly in a darkened room on a calibrated Microsoft Surface Display at 3 ft. (91.44 cm). A cone specific letter appears in the center of the display and the subject uses a mouse to choose the letter seen from an adjacent matching display. A response driven staircase determines the lowest red, green and blue cone contrast seen (cone CS; 100-point scale) with testing conducted with and without CCLs and placebo lenses.
5. \*Cone Contrast Naming Test (CCNT) administered binocularly at 3 ft. in a darkened room on a calibrated Microsoft Surface Display. Red, green and blue cone specific letters and black/white luminance letters of varying contrast appear in the display center and the subject identifies the letters seen and their color names with the lowest contrast seen (cone CS) and number and type of color names correct scored on a 100-point scale. Letter sequence and testing with and without CCLs and placebo lenses.

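### Week-two carry-over in the CCL-first subjects cannot show how long any neuro-adaptive change lasts, because persistence after CCL wear ends is confounded with practice and period

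*Combined protocol and SAP*

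**What the plan says.** The Statistical Design and Analysis section states that the crossover trial "will be used to assess the immediate and long-term effects on color vision of CCLs in CVDs". It concedes that CCL exposure in week one may carry over into the placebo week, and treats this as an advantage: "we believe this may offer additional insight into the time course and longevity of any effects from presumed neuro-adaptive changes". The analysis is within- and between-subject ANOVA with corrected post-hoc t-tests. No period, sequence or carry-over term is named.

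The Background also refers to long-term changes and describes the randomised crossover as a design "which we are conducting to definitively address the findings presented in prior studies". One earlier study is described in two ways: in Purpose as one "which only reported 12 day results", and in the Background as "Extended use by CVDs for two weeks demonstrated improvements in red-green color perception even without wearing the glasses at the 2-week testing point".

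The Hypothesis is narrower. It concerns immediate improvement, improvement after one week of daily wear, and whether that improvement is still present when the lenses are off.

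Methods randomises half of the 20 colour-deficient subjects to each lens first. Subjects are tested with and without lenses at baseline, asked to wear the lens for at least three hours a day, and retested with and without it 7 days later. Within a further 1 to 3 days they "cross-over to the lens not yet worn, undergo testing, and be tested again 7 days later". No later test is planned. Methods thus implies four test occasions, whereas Subject Criteria schedules three visits and item 10 of Methods refers to three sessions.

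**The concern.** Longevity means what remains after CCL wear has stopped. Placebo-first subjects finish the study on their last CCL day, so they contribute nothing on this. CCL-first subjects are followed through the placebo week, but at the final test nobody without a CCL week has had the same number of repeat tests. The asterisked tests include letter recognition, colour naming and a timed symbol search, where improvement with repetition is plausible. Practice or period gain in 10 subjects could then be reported as lasting neuro-adaptive change.

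A second, smaller issue is wording. Seven days of wear is a one-week exposure, as the Hypothesis says. Calling it long-term invites readers to set a null result at day 7 against a finding from 12 days or two weeks of wear, which this schedule does not test.

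**Working it through.** The documents give no figure for practice gain, retest variability or expected persistence, so there is no stated figure to reproduce. The check is a count of the schedule followed by an illustration.

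**Inputs from the documents.** 20 subjects, 10 per sequence; 7 days per lens at a requested minimum of 3 hours a day; a gap of 1 to 3 days (all Methods). Earlier wear of 12 days (Purpose) or two weeks (Background). Test occasions: four (Methods schedule) or three (Subject Criteria; Methods item 10).

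**Assumed.** G is the true no-lens gain from a CCL week; p is the practice gain per repeat test, the same in both groups; CCL wear stops at the day-7 test in the CCL-first group.

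**Step 1: exposure.** 7 × 3 = 21 hours per lens at the requested minimum. 7/12 = 58% and 7/14 = 50% of the earlier wear. If adaptation grows linearly, day 7 shows 58% of a 12-day effect. If it grows exponentially with time constant t days, the share is (1 − e^(−7/t)) / (1 − e^(−12/t)): 92% for t = 3, 77% for t = 7, 68% for t = 14. The growth forms and time constants are assumptions.

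**Step 2: who can be compared, without lenses.**

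| Occasion | CCL-first (10) | Placebo-first (10) | Like-for-like? |
|---|---|---|---|
| Day 7 | CCL week done | placebo week done | yes |
| Crossover, before second lens (if a separate visit) | 1–3 days off CCLs | no CCL week yet | yes |
| Final test | 1 + 7 = 8 to 3 + 7 = 10 days off CCLs | CCL week just ended, 0 days off | no |

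If crossover takes place at the day-7 visit, the middle row disappears and the final test falls 7 days after CCL wear. Either way, the final row has no concurrent control.

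**Step 3: size of the confounding.** Suppose the CCL gain is wholly lost by the final test. In the CCL-first group the no-lens change from baseline is G + p at day 7 (one repeat). At the final test it is 3p with four occasions or 2p with three. The apparent share persisting, when the truth is 0%, is:

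| p | four occasions, 3p/(G + p) | three occasions, 2p/(G + p) |
|---|---|---|
| 0.1G | 0.3/1.1 = 27% | 0.2/1.1 = 18% |
| 0.2G | 0.6/1.2 = 50% | 0.4/1.2 = 33% |
| G/3 | 1/(4/3) = 75% | (2/3)/(4/3) = 50% |

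**Step 4: the contrast that is controlled.** At day 7, CCL-first minus placebo-first is (G + p) − p = G. At a separate crossover visit, with R the gain still remaining, it is (R + 2p) − 2p = R. Practice common to both groups cancels.

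**Step 5: precision of that contrast.** At an assumed two-sided 5% level and 80% power, 10 versus 10 detects a standardised difference of 1.32 before baseline adjustment; power for a difference of 0.8 is 39%. A paired comparison in all 20 would detect 0.66, but in units of the standard deviation of differences, so the two are not on one scale. The paired comparison also takes the CCL-first subjects' placebo value after CCL wear, where carry-over is expected.

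**The case against.** A reader might infer that persistence is seen only in the CCL-first half, or has no control anywhere. The documents do not support that. Persistence in the sense of the Hypothesis, performance without lenses after one week of wear, is tested in both sequences, and in week one it has a randomised placebo control with equal prior testing. The gap concerns the stretch after the crossover.

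A reader might also infer that the trial claims to replicate or refute the 12-day result. It does not say so. The definitive claim is tied to the registered randomised design and to prior studies in general, including the team's own. Purpose gives a reason for a shorter exposure: "potential changes in the brain can occur from wearing these lenses in as little as 1 week or even less". The longevity statement is hedged as something that may offer insight. These points stand and make the duration issue one of wording. They do not rescue *long-term*, which is unhedged and wider than the Hypothesis.

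Practice might also be estimated. Under a constant p, placebo-first no-lens scores give p at day 7 and 2p at a separate crossover visit, which could be subtracted. The plan names no such analysis, and the last repeat is never observed in subjects without a CCL week, so the correction rests on extrapolation. The planned comparison of normal with defective cones could expose a general practice gain, but as a correction it needs practice to be equal for both cone types.

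Finally, the values of p and the total loss of G are assumptions, and the 27% to 75% range needs four occasions. Both visit counts are therefore shown.

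**Conclusion.** The concern holds for persistence beyond the end of CCL wear, read from week two of the CCL-first sequence. That result rests on 10 subjects with no concurrent control at the final test and is confounded with practice and period. In the illustration, a true persistence of zero appears as 27% to 75% with four test occasions, or 18% to 50% with three, given complete loss of G and practice of 0.1G to G/3 per repeat. These figures show how large the distortion could be; they do not estimate it.

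The concern does not extend to no-lens performance at the end of week one, which the design can test fairly. Nor is one week of wear wrong in itself: it matches the Hypothesis. What needs changing is the *long-term* label and any suggestion that a null at day 7 settles a finding from 12 days or two weeks of wear.

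**What to change.** 1. In Statistical Design and Analysis and in the Background, replace *long-term* with *one-week*. State that a null at day 7 does not contradict the 12-day or two-week finding.
2. Name as the persistence analysis the no-lens score at the end of week one, CCL-first minus placebo-first, adjusted for the day-0 no-lens score. Use day 7, or the crossover visit before the second lens goes on if that is a separate visit, and fix the choice in advance. Keep the randomised with/without-lens order in Methods: forcing the no-lens test first would tie the second lens's immediate effect to within-visit practice or fatigue.
3. Report later CCL-first no-lens scores as exploratory, uncontrolled description.
4. Reconcile the visit count (three in Subject Criteria and Methods item 10, four occasions implied by the Methods schedule) and the 12-day and two-week descriptions of the same cited study.

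The cost is protocol wording and one prespecified contrast on tests already planned, with no extra subjects. The downside is precision. The estimate is 10 versus 10, with a detectable standardised difference of about 1.3 before adjustment under the assumptions in the working; baseline adjustment improves on this by an amount the documents do not allow us to state. The claims also become more modest.

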## Background and Review of Literature

Normal color vision (CVN) depends on normal red, green, and blue sensitive cone photoreceptors. 8% of males and 0.5% (1/200) females are color vision deficient (CVD), a non progressive hereditary condition in which the red or green cone is missing, or more commonly shifted in peak color sensitivity making it more difficult to tell colors apart and correctly identify colors (1,2). In addition to hereditary CVD, color vision can be decreased at a clinical or subclinical level as an early sign of ocular, systemic and/or neurological disease. (3-7). CVN is required for aviation, military specialties, transportation, and law enforcement wherein color identification and discrimination may be the only cue for critical decisions (3,4). A novel approach using notch filter spectacles (selective wavelength blocking filters to increase differences in stimulation to red and green cones) was implemented by EnChroma®. Extended use by CVDs for two weeks demonstrated improvements in red-green color perception even without wearing the glasses at the 2-week testing point indicating possible neuro-adaptive/brain changes (8). We extended this evaluation by including both threshold (just visible) and supra-threshold testing (readily visible) and found similar results (11). However, a major difference was that our testing was cone specific allowing us to more specifically compare findings from the defective and normal cones in red and green cone CVDs. Limitations of our initial pilot study included a large variability in the type of CCL glasses used (outdoor vs. indoor, red vs. green specific). In addition, since we previously demonstrated enhanced binocular VEP responses in CVDs suggesting neural compensation without CCLs (10), we will be conducting monocular VEP and ERG cone specific tests on all subjects to better identify CCL induced immediate and long term changes on retinal, optic nerve and cortical objective responses. Finally, no study thus far using these CCLs has adhered to the tenets of a registered randomized clinical control cross-over design which we are conducting to definitively address the findings presented in prior studies.

## Significance

This research has potential significant impact on occupational uses of CCLs, use of CCLs in acquired CVD, and to significantly expand our knowledge of how neural plasticity can occur in adulthood, a common theme in multiple diseases including glaucoma, Alzheimer and Parkinson disease.

### Potential Benefit to Subjects

CVD subjects will learn very specific information about the type and severity of their color deficiency and may benefit from the color vision correcting lenses.

### Privacy and Confidentiality. Security Measures for Data Storage and Collection

A PW protected cloud-based drive will be used for deidentified data to be accessible ONLY to the research team. The list of participants with identifiable PHI will be stored by the PI on a single PW protected encrypted computer and in a locked filing cabinet only accessible to the PI or designees when needed.

## Methods

After study briefing and subject provision of written informed consent, the following sequence of tests will be conducted. Half of the 20 CVD subjects will be randomized to initial treatment (CCLs) and half to initial or control groups (placebo neutral lenses). Baseline testing will be conducted with and without the lenses, then be requested to wear the lenses for a minimum of three hours per day, followed by retesting with/without lenses 7 days later. On the next 1-3 days the subject will then: cross-over to the lens not yet worn, undergo testing, and be tested again 7 days later. Neither subjects or Interns administering the tests will be aware of which lenses the subject is wearing (double-blind clinical trial). On all tests the order of testing with with and without lenses will be randomized across subjects to control for potential order effects. Those tests marked by an asterisk will be retested on CVD subjects during each session. Additional controls for order effects are specified below.

1. Precision Vision, Inc. "Super Vision Test" to measure high contrast visual acuity (VA) and Small Letter Contrast Sensitivity (CS) in right and left eyes at 4m in a darkened room; only at baseline.
2. Oculus HMC anomaloscope to diagnosis CVN and CVD subjects; only at baseline.
3. Ishihara 15-plate (14 testable plates, one demo) color vision book test to diagnose CVN vs. CVD; only at baseline.
4. \*Cone Specific Contrast Sensitivity Test (CCT, Innova Systems, Inc.) administered binocularly in a darkened room on a calibrated Microsoft Surface Display at 3 ft. (91.44 cm). A cone specific letter appears in the center of the display and the subject uses a mouse to choose the letter seen from an adjacent matching display. A response driven staircase determines the lowest red, green and blue cone contrast seen (cone CS; 100-point scale) with testing conducted with and without CCLs and placebo lenses.
5. \*Cone Contrast Naming Test (CCNT) administered binocularly at 3 ft. in a darkened room on a calibrated Microsoft Surface Display. Red, green and blue cone specific letters and black/white luminance letters of varying contrast appear in the display center and the subject identifies the letters seen and their color names with the lowest contrast seen (cone CS) and number and type of color names correct scored on a 100-point scale. Letter sequence and testing with and without CCLs and placebo lenses.
7. \*Cone specific VA, small letter CS, and large letter CS administered on a calibrated Microsoft Surface Display using computer generated letter charts at 3 ft. (91.44 cm) in a darkened room. CVD subjects will be tested with/without CCLs and placebo in separate session with VA and CS scored as the number of letters read correctly in log MAR units for VA and log CS for cone CS.
8. \*Cone Specific Supra-threshold Color Matching Test administered on a calibrated Microsoft Surface Display binocularly in a darkened room at 60 cm for each session. Red Cone Test for red CVDs: a red letter "E" will be displayed on the left half of the screen and three green Letter E's on displayed vertically on the right half of the screen with contrasts of 16 – 8% in 0.15 log steps with contrast order randomized and numbered letters numbered 1 - 3. On each of three trials the subject will match the perceived visibility and brightness of the red letter (displayed individually in randomized contrasts ranging from 16 – 8% in 0.15 log steps) to the number of the green letter it matches. The subject will then conduct the same task matching each green letter shown individually on the left to a series of three green letters on the right. The Green Cone Test for green cone CVDs will require the subject to match a single green cone letter to a series of red cone letters on the right using the same contrasts specified above, followed a match between red to red. As in prior studies, it is anticipated that CVDs will match higher contrasts of their defective cone type to lower contrasts of their normal cone type. Testing will be conducted with/without CCLs.
9. \*The "Cockpit" color identification test displays 35 small colored airplane symbols with five of each of seven colors (red, green, blue, purple, yellow, orange, grey) on a 17" calibrated LCD display. On each trial the subject will be told to eliminate one of the four colors, and then immediately uses the mouse to click on the five airplane symbols of the specified color as fast as possible. On each of the seven trials the 35 symbols appear in randomized placement on a black background and the program tabulates the time taken to complete all five symbols, total time and errors made. All subjects will be tested binocularly at 50-60 cm with and without the CCLs.
10. \*Cone specific visual brainwaves (visual-evoked potentials, VEPs, 10,11) and flash and pattern eye waves (electroretinograms, ERGs) will be recorded monocularly from the subject's stated preferred eye with the fellow eye occluded by an eye patch. For VEPs, ear clip electrodes will be applied to each earlobe with conductive electrode paste after cleaning each earlobe with an electrode skin cleanser (Nu-Prep, Diagnosys, LLC) and an alcohol pad. The back of the head will be cleaned with the same agents 1cm above the inion and a gold cup electrode will be taped to this active site with conductive paste and secured by a headband. The active electrode will be at the back of the head with reference electrode on the ipsilateral earlobe and ground on the opposite earlobe. VEPs will be recorded to red, green and blue cone checkerboard patterns presented at

57 cm in a darkened room in pattern onset mode (10,11). Pattern onset ERGs will be recorded at 57 cm from the same display with check sizes of 3 degrees for red and green cones and a 5 degree check size for blue cones in pattern onset mode. Flash ERGs will recorded at a distance of 30 cm from the display to fill the atient's field with an onset red, green and blue cone flash ERG with the subject supported by a chin and headrest. For ERGs the ear clip electrodes will again serve as reference and ground, and the active electrode will be an FDA approved disposable DTL micro-fiber electrode (Diagnosys, LLC; FDA Approved Class II <https://www.accessdata.fda.gov/scripts>) which is attached to adhesive discs on each end which are affixed to the corners (inner and outer canthi) of each eye. Prior to electrode application, 1 drop of the ocular anesthetic (Proparacaine Hydrochloride Ophthalmic Solution [www.accessdata.fda.gov/scripts/cder/ob/results\\_product.cfm?AppType=A&AppNo=040277#22240](http://www.accessdata.fda.gov/scripts/cder/ob/results_product.cfm?AppType=A&AppNo=040277#22240)) will be instilled after ensuring that the subject has no allergy to this medication. The adhesive discs will then be attached to the canthi of each eye and the filament will be draped over the white of the eye below the limbus (lower border of colored part of eye). If the subject does not wish to use this electrode an infraorbital skin electrode (gold cup with electrode paste) will be taped on the lower lid directly below the center of the eye. During testing, electrode impedance (resistance) will be maintained at no more than 5 kilohms in accord with international standards ([www.iscev.org](http://www.iscev.org)). ERG and VEP order of testing will be randomized across subjects and this testing will be conducted at each of the three sessions in CVD.

